## 1.2 Research Hypothesis

Treatment with ulocuplumab in combination with nivolumab will be safe, tolerable and demonstrate clinically meaningful efficacy in subjects with advanced or metastatic solid tumors.

## 1.3 Objectives(s)

### 1.3.1 Primary Objectives

- Stage 1: To identify the recommended dose and schedule of ulocuplumab, based on safety and efficacy, in combination with nivolumab in subjects with advanced or metastatic tumors
- Stage 2: To evaluate the efficacy, separately by tumor type, based on objective response rate (ORR) or overall survival (OS; randomized Phase 2 study in PAC only), of ulocuplumab combined with nivolumab in subjects with advanced or metastatic tumors

### 1.3.2 Secondary Objectives

- To assess the safety and tolerability of ulocuplumab combined with nivolumab, in subjects with advanced or metastatic tumors
- To assess progression-free survival (PFS) with ulocuplumab combined with nivolumab, separately by tumor type, in subjects with advanced or metastatic tumors

### 1.3.3 Exploratory Objectives

- 
- 
- 
- 
- 
- 
- 

## **2 ETHICAL CONSIDERATIONS**

### **2.1 Good Clinical Practice**

This study will be conducted in accordance with Good Clinical Practice (GCP), as defined by the International Conference on Harmonisation (ICH) and in accordance with the ethical principles underlying European Union Directive 2001/20/EC and the United States Code of Federal Regulations, Title 21, Part 50 (21CFR50).

The study will be conducted in compliance with the protocol. The protocol and any amendments and the subject informed consent will receive Institutional Review Board/Independent Ethics Committee (IRB/IEC) approval/favorable opinion prior to initiation of the study.

All potential serious breaches must be reported to BMS immediately. A serious breach is a breach of the conditions and principles of GCP in connection with the study or the protocol, which is likely to affect, to a significant degree, the safety or physical or mental integrity of the subjects of the study or the scientific value of the study.

Personnel involved in conducting this study will be qualified by education, training, and experience to perform their respective tasks.

This study will not use the services of study personnel where sanctions have been invoked or where there has been scientific misconduct or fraud (eg, loss of medical licensure, debarment).

### **2.2 Institutional Review Board/Independent Ethics Committee**

Before study initiation, the investigator must have written and dated approval/favorable opinion from the IRB/IEC for the protocol, consent form, subject recruitment materials (eg, advertisements), and any other written information to be provided to subjects. The investigator or BMS should also provide the IRB/IEC with a copy of the Investigator Brochure or product labeling information to be provided to subjects and any updates.

The investigator or BMS should provide the IRB/IEC with reports, updates and other information (eg, expedited safety reports, amendments, and administrative letters) according to regulatory requirements or institution procedures.

### **2.3 Informed Consent**

Investigators must ensure that subjects are clearly and fully informed about the purpose, potential risks, and other critical issues regarding clinical studies in which they volunteer to participate.

In situations where consent cannot be given to subjects, their legally acceptable representatives (as per country guidelines) are clearly and fully informed about the purpose, potential risks, and other critical issues regarding clinical studies in which the subject volunteers to participate.

BMS will provide the investigator with an appropriate (ie, Global or Local) sample informed consent form which will include all elements required by ICH, GCP and applicable regulatory requirements. The sample informed consent form will adhere to the ethical principles that have their origin in the Declaration of Helsinki.

Investigators must:

- 1) Provide a copy of the consent form and written information about the study in the language in which the subject is most proficient prior to clinical study participation. The language must be non-technical and easily understood
- 2) Allow time necessary for subject or subject's legally acceptable representative to inquire about the details of the study
- 3) Obtain an informed consent signed and personally dated by the subject or the subject's legally acceptable representative and by the person who conducted the informed consent discussion
- 4) Obtain the IRB/IEC's written approval/favorable opinion of the written informed consent form and any other information to be provided to the subjects, prior to the beginning of the study, and after any revisions are completed for new information
- 5) If informed consent is initially given by a subject's legally acceptable representative or legal guardian, and the subject subsequently becomes capable of making and communicating his or her informed consent during the study, consent must additionally be obtained from the subject
- 6) Revise the informed consent whenever important new information becomes available that is relevant to the subject's consent. The investigator, or a person designated by the investigator, should fully inform the subject or the subject's legally acceptable representative or legal guardian, of all pertinent aspects of the study and of any new information relevant to the subject's willingness to continue participation in the study. This communication should be documented

The confidentiality of records that could identify subjects must be protected, respecting the privacy and confidentiality rules applicable to regulatory requirements, the subjects' signed ICF and, in the US, the subjects' signed HIPAA Authorization.

The consent form must also include a statement that BMS and regulatory authorities have direct access to subject records.

The rights, safety, and well-being of the study subjects are the most important considerations and should prevail over interests of science and society.

### **3 INVESTIGATIONAL PLAN**

#### **3.1 Study Design and Duration**

This is an open-label, multi-center phase 1/2 study of ulocuplumab in combination with nivolumab designed to independently evaluate the safety and efficacy in subjects with SCLC and PAC. The study design consists of a Dose Evaluation Phase (Stage 1) that will include a DLT evaluation period to identify the MTD. If the maximum dose level (DL3) is identified as the MTD, a parallel evaluation of three cohorts will assess two dose levels (800 mg, 1600 mg) and an additional schedule for 1600 mg (every 2 weeks). If 2 or more DLT are seen with any dose during the DLT evaluation period, a lower dose will be evaluated as a single arm. A recommended dose will be selected based on the safety and efficacy data from Stage 1 and will

[figure not shown]
proceed to Dose Expansion in the form of a Simon optimal 2-stage like design or a randomized Phase 2 study with comparative arm if high efficacy is observed.

The study will consist of Screening, Treatment, and Follow-up. All subjects will undergo a screening period to determine eligibility within 28 days prior to initial dosing. During the treatment phase, ulocuplumab will be administered weekly or every two weeks (1600 mg dose only) and nivolumab will be administered every two weeks. The treatment period will continue until disease progression or occurrence of unacceptable toxicity. During follow-up, subjects will be monitored for disease activity and safety. The duration of the study is anticipated to be approximately 2 years.

The study design schematic is presented in Figure 1.

[figure not shown]
**Figure 1: Study Design Schematic**

**Dose Evaluation Phase (Stage 1)**

[figure not shown]
**Dose Expansion Phase (Stage 2)**

**Simon 2-stage (per tumor type):**

OR

**Randomized Phase 2 (per tumor type):**

### 3.1.1 Dose Evaluation Phase (Stage 1)

The Dose Evaluation Phase will consist of a DLT evaluation period followed by an evaluation of up to three cohorts with various doses and schedules of ulocuplumab combined with nivolumab. The DLT evaluation period will be conducted in the first 3-6 subjects with either PAC or SCLC at dose level 1 (DL1; 400 mg weekly ulocuplumab combined with nivolumab), followed by 3-6 subjects each with PAC and SCLC at DL2 (800 mg weekly ulocuplumab combined with nivolumab), followed by 3-6 subjects each with PAC and SCLC at DL3A (1600 mg weekly ulocuplumab combined with nivolumab) for 6 weeks. For DL1, both tumor types will be combined for the safety evaluation. If 2 or more DLT are observed at DL1, de-escalation to DL-1 will occur (200 mg weekly ulocuplumab combined with nivolumab). For all other dose levels, each tumor type will be evaluated for safety independently in the event that tumor specific AE may emerge.

Enrollment during the DLT evaluation phase will allow for concurrent accrual of up to 6 subjects in each dose/tumor cohort (ie, Rolling Six design). This design allows for 3-6 evaluable subjects to contribute to the DLT evaluation depending upon how many are enrolled and still being evaluated during the DLT period. Decisions as to whether to enroll a new participant onto the current dose level or next highest dose level will be based on available data at the time of new participant enrollment. Study stopping rules for the DLT evaluation period and the decision to proceed with the Dose Evaluation Phase include the following:

- Enrollment in the active cohort will proceed if there are:
  - < 3 subjects enrolled, up to a maximum of 6 subjects
  - 1 DLT in 2 or up to 5 subjects evaluable for toxicity
- Enrollment in the active cohort will be paused if there are:
  - a maximum of 6 subjects enrolled (including evaluable and non-evaluable)
- Active cohort is deemed intolerable and enrollment will be stopped for evaluation if there are:
  - ≥ 2 DLT in up to 6 subjects evaluable for toxicity
- Active cohort is deemed tolerable and enrollment will proceed to next step if there are :
  - 0 DLT in 3 or up to 6 subjects evaluable for toxicity
  - 1 DLT in 6 subjects evaluable for toxicity
- Subjects who are not evaluable for DLT (ie, discontinuation due to disease progression) will be replaced with a concurrently enrolled subject

**Table 3.1.1-1: Dose Levels for Ulocuplumab and Nivolumab**

Dose Level	Ulocuplumab	Nivolumab
DL-1	200 mg weekly	3 mg/kg every 2 weeks
DL1	400 mg weekly	3 mg/kg every 2 weeks
DL2	800 mg weekly	3 mg/kg every 2 weeks
DL3A	1600 mg weekly	3 mg/kg every 2 weeks

DL3B	1600 mg every 2 weeks	3 mg/kg every 2 weeks
------	-----------------------	-----------------------

Depending on the number of DLT observed during the DLT evaluation period, escalation or de-escalation of ulocuplumab may be warranted. Dose escalation/de-escalation at the 800 mg weekly and 1600 mg weekly ulocuplumab dose levels will occur independently for each tumor type. No dose modification of nivolumab will be allowed in this study.

- If the toxicity at DL1 and DL2 and DL3A are acceptable, enrollment will proceed with three randomized cohorts (DL2, DL3A, and DL3B) to complete Stage 1
- If the toxicity at DL3A is unacceptable, enrollment will proceed at DL2 to complete Stage 1
- If the toxicity at DL2 is unacceptable, enrollment will proceed at DL1 to complete Stage 1
- If the toxicity at DL1 is unacceptable, a new DLT evaluation period will proceed at DL-1
- If the toxicity of DL-1 is unacceptable, enrollment will stop for that tumor type
- If the toxicity at DL-1 is acceptable, enrollment will proceed at DL-1 to complete Stage 1 at a single dose level

### **3.1.2 Decision Rules to Proceed with Dose Expansion Phase**

An interim analysis (IA) will be carried out when all subjects in the Dose Evaluation Phase in an individual tumor type have at least three months of treatment, or discontinued prematurely. This IA will be conducted independently for each tumor type. Investigator-assessed ORR will be used to guide the decision making for the Stage 2 portion of the study. However, all available efficacy and safety data will be used to select the recommended dose that will be further evaluated in the Dose Expansion Phase. Furthermore, if the level of efficacy observed at the recommended dose in the Dose Evaluation Phase does not warrant stopping evaluation of that tumor type, it will be used to select the appropriate Expansion Phase study design, either proceeding with a Simon 2-stage-like design or conducting a randomized Phase 2 study with comparative arm. The efficacy thresholds used for the IA analysis are based on the preliminary efficacy data from the ongoing Phase 1/2 study evaluating nivolumab monotherapy in SCLC and PAC and the level of activity reported for 2L options. The determination of low, moderate or high efficacy will be based primarily on the response rates observed with ulocuplumab and nivolumab, but the totality of available safety and efficacy data will be considered. For further information on the interim analysis and the efficacy thresholds used for decision rules, please refer to [section 8.5](#).

- If the number of responders per tumor type at the recommended dose level is consistent with low efficacy, the evaluation of that tumor type will be placed on hold pending final review of the data.
- If the number of responders per tumor type at the recommended dose level is consistent with moderate efficacy, the Dose Expansion Phase will continue with a single-arm evaluation.
- If the number of responders per tumor type at the recommended dose level is consistent with high efficacy, the Dose Expansion Phase will be continue with a randomized Phase 2 study with comparative arm.

**Table 3.1.2-1: Stage 1 Efficacy Threshold For Each Tumor Type**

Efficacy Threshold	SCLC	PAC
Low	≤ 3 responders / 19 subjects	≤ 1 responders / 21 subjects
Moderate	4-8 responders / 19 subjects	2-5 responders / 21 subjects
High	≥ 9 responders / 19 subjects	≥ 6 responders / 21 subjects

### **3.1.3 Dose Expansion Phase (Stage 2)**

Based on the results of the IA, the Dose Expansion Phase will consist of a second stage of a Simon 2-stage like single arm study (moderate efficacy) or a randomized Phase 2 study with comparative arm (high efficacy).

The second stage of a Simon 2-stage like design will expand enrollment at the recommended dose level in a single arm study. An additional 25 SCLC subjects and 20 PAC subjects will be enrolled to complete this evaluation. The primary endpoint will be investigator-assessed ORR for both tumor types and PFS will be considered a secondary endpoint.

The randomized Phase 2 study will compare the combination therapy at the recommended dose level versus a comparative arm appropriate for that tumor type. The primary endpoint of this study will be dictated by the tumor type, where ORR is the endpoint for a randomized Phase 2 study in SCLC and OS for a randomized Phase 2 study in PAC. For ORR, independent radiology review committee (IRRC) will perform blinded independent review of the imaging per RECIST 1.1 criteria. More details regarding the randomized Phase 2 for each tumor type are described below.

#### **SCLC**

A randomized Phase 2 study with comparative arm in SCLC will compare the recommended dose of ulocuplumab combined with nivolumab versus nivolumab monotherapy. The main goal of this comparison will be to determine whether the combination therapy is superior to nivolumab monotherapy. The primary endpoint of this study will be evaluation of IRRC assessed ORR. Safety, tolerability and PFS will be considered as secondary endpoints. A randomized Phase 2 study would require an additional 50 subjects per arm (ie. 100 for the two arms). The SCLC subjects included in the Dose Evaluation Phase will not be part of the efficacy analysis of the randomized Phase 2 study. A stratification factor will be used for this portion of the study to balance recruitment and will include performance status (ECOG 0 vs 1). For additional statistical considerations for the randomized Phase 2 study with comparative arm in SCLC subjects, please see [Section 8](#).

#### **PAC**

A randomized Phase 2 study with comparative arm in PAC will compare the recommended dose of ulocuplumab combined with nivolumab versus Investigator’s Choice 2L chemotherapy. The main goal of this comparison will be to determine if ulocuplumab plus nivolumab combination therapy is superior to 2L chemotherapy. The primary endpoint of this study will be OS. Safety,

tolerability and PFS will be considered as secondary endpoints. For PAC, a randomized Phase 2 study would require an additional 125 subjects per arm (ie. 250 for the two arms). [REDACTED]. The PAC subjects included in the Dose Evaluation Phase will not be considered in the analysis of the randomized Phase 2 study. Investigator's choice chemotherapy options in this study are based on NCCN guidelines for PAC and include the following.

- Subjects that have failed FOLFIRINOX or other fluoropyrimidine based regimens can consider gemcitabine-based therapies for this study
- Subjects that have failed gemcitabine based regimens can consider fluoropyrimidine-based regimens for this study

Stratification factors will be used for this portion of the study and will include performance status (ECOG 0 vs 1) and type of chemotherapy used in the first line setting (fluoropyrimidine-containing vs gemcitabine-containing regimens). For additional statistical considerations for the randomized Phase 2 study with comparative arm in PAC subjects, please see [Section 8](#).

### **3.1.4 Dose Limiting Toxicity**

The incidence of DLT(s) assessed in the first 3-6 evaluable subjects per tumor type (if applicable) during the first 6 weeks will be used to initially determine whether a dose level is tolerable. A subject will be considered evaluable for DLT if they have received at least 5 out of 6 ulocuplumab doses and at least 2 out of 3 nivolumab doses in a 6 week dosing period or experienced a DLT. DLT should not be AE considered by the investigator to be disease related. The following drug-related AE (whether related to one or both agents) will be considered a DLT:

- Any Grade  $\geq 3$  drug-related non-hematological AE, including the following laboratory abnormalities
  - If a subject has baseline Grade  $\leq 1$  AST, ALT, or total bilirubin, a drug-related Grade  $\geq 3$  toxicity will be considered a DLT
  - If a subject has baseline Grade 2 AST or ALT, drug-related elevations in AST and/or ALT  $> 2x$  baseline or a maximum of  $> 8x$  ULN will be considered a DLT
- Any Grade 4 drug-related hematological AE or hematological or non-hematological laboratory abnormality with the following exceptions:
  - Grade 4 amylase or lipase not associated with symptoms or clinical manifestations
  - Grade 4 lymphocytopenia not associated with symptoms or clinical manifestations
- Any drug-related AE that results in dose reduction of ulocuplumab during the DLT period
- Any drug related AE that results in dose delay of ulocuplumab  $> 14$  days during DLT period
- Any toxicity managed by discontinuation of ulocuplumab (see [section 4.5.3.1](#))
- Any toxicity managed by discontinuation of nivolumab (see [section 4.5.3.2](#))

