##### **4.5.1 Dose Delays and Interruptions**

###### **4.5.1.1 Ulocuplumab Dose Delay**

Investigators should, whenever possible, determine which medication is causing the toxicity and delay or dose reduce ulocuplumab and/or delay nivolumab, as applicable. If ulocuplumab is delayed due to an AE, nivolumab dosing may continue at the discretion of the Investigator. Ulocuplumab should be delayed for the following:

- Any Grade  $\geq 3$  drug-related AE, including laboratory abnormalities except for Grade 3 AEs that do not require nivolumab dose delay (see [section 4.5.1.2](#))

If the decision is to resume ulocuplumab dosing, the subject should restart treatment on the next regularly scheduled ulocuplumab dosing visit. Skipped doses are not to be replaced. If treatment is delayed > 6 weeks, the subject must be permanently discontinued from ulocuplumab therapy.

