#### **4.5.1.2 Nivolumab Dose Delay**

Investigators should, whenever possible, determine which medication is causing the toxicity and delay or dose reduce ulocuplumab and/or delay nivolumab, as applicable. If nivolumab is delayed due to an AE, ulocuplumab dosing should also be delayed. Nivolumab should be delayed for the following:

- Any Grade  $\geq 2$  non-skin, drug-related AE, with the following exceptions:
  - Grade 2 drug-related fatigue or laboratory abnormalities do not require a treatment delay
- Any Grade 3 skin drug-related AE
- Any Grade  $\geq 3$  drug-related laboratory abnormality, with the following exceptions for thrombocytopenia, lymphocytopenia, AST, ALT, total bilirubin or asymptomatic amylase or lipase:
  - Grade 3 thrombocytopenia  $< 7$  days (not associated with Grade  $\geq 2$  hemorrhage) does not require dose delay
  - Grade 3 lymphocytopenia not associated with symptoms or clinical manifestations does not require dose delay. It is recommended to consult with the BMS Medical Monitor for Grade 3 lymphocytopenia.
  - Grade 3 drug-related amylase or lipase abnormality that is not associated with symptoms or clinical manifestations of pancreatitis does not require dose delay. It is recommended to consult with the BMS Medical Monitor for Grade 3 amylase or lipase abnormalities
  - If a subject has baseline AST, ALT, or total bilirubin that is within normal limits, delay dosing for drug-related Grade  $\geq 2$  toxicity
  - If a subject has baseline AST, ALT, or total bilirubin within the Grade 1 toxicity range, delay dosing for drug-related Grade  $\geq 3$  toxicity
  - If a subject has baseline AST or ALT within the Grade 2 toxicity range, delay dosing for drug-related elevations in AST and/or ALT  $> 2x$  baseline or a maximum of  $> 8x$  ULN
- Any adverse event, laboratory abnormality, or intercurrent illness which, in the judgment of the investigator, warrants delaying the dose of study medication

If the decision is to resume nivolumab dosing, the subject should restart treatment on the next regularly scheduled nivolumab dosing visit. Skipped doses are not to be replaced. If treatment is delayed  $> 6$  weeks, the subject must be permanently discontinued from all study therapy, except as specified in [Section 4.5.3.2](#).

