**Table 4.5.2.1-1: Ulocuplumab Dose Modification Criteria**

Adverse Event	Dose Delay (refer to section 4.5.1.1)	Criteria to Resume Ulocuplumab Treatment			
		For DL-1	For DL1	For DL2	For DL3A/3B
Any Gr ≥ 3 drug-related AE, including laboratory abnormalities, except for Grade 3 hematologic AEs listed below or other exceptions listed in section 4.5.1	Hold ulocuplumab until return to baseline or Grade ≤ 1, whichever is lower	1st event: Discontinue ulocuplumab	1st event: Resume at 200 mg weekly	1st event: Resume at 400 mg weekly	1st event: Resume at 800 mg weekly
			2nd event: Discontinue ulocuplumab	2nd event: Resume at 200 mg weekly	2nd event: Resume at 400 mg weekly
				3rd event: Discontinue ulocuplumab	3rd event: Discontinue ulocuplumab
Any Gr3 drug-related neutropenia, Gr3 thrombocytopenia > 7 days	Hold ulocuplumab until return to baseline or Grade ≤ 1, whichever is lower	2nd event: Discontinue ulocuplumab	1st event: Resume at 200 mg weekly	1st event: Resume at 400 mg weekly	1st event: Resume at 800 mg weekly
			3rd event: Discontinue ulocuplumab	2nd event: Resume at 200 mg weekly	2nd event: Resume at 400 mg weekly
				3rd event: Discontinue ulocuplumab	3rd event: Discontinue ulocuplumab
Gr4 asymptomatic lipase or amylase elevations	Hold ulocuplumab until return to baseline or Grade ≤ 1, whichever is lower	All events: Resume at same dose. Consult with BMS Medical Monitor if recurrent or sustained.			

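### Asymptomatic Grade 4 lymphocytopenia is excepted as a DLT and from required discontinuation, yet Table 4.5.2.1-1 directs a ulocuplumab reduction or, at DL-1, a stop

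*Protocol*

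**What the plan says.** Five parts of the protocol bear on one event: drug-related Grade 4 lymphocytopenia without symptoms or clinical manifestations.

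- **3.1.4, DLT definition.** The Grade 4 bullet has two exceptions: asymptomatic amylase or lipase, and "Grade 4 lymphocytopenia not associated with symptoms or clinical manifestations". Later bullets stand alone and carry no exception, including "Any drug-related AE that results in dose reduction of ulocuplumab during the DLT period". A delay of ulocuplumab beyond 14 days and a toxicity managed by stopping either drug are also DLTs. Evaluability sets a dosing minimum: "received at least 5 out of 6 ulocuplumab doses and at least 2 out of 3 nivolumab doses in a 6 week dosing period". A subject with a DLT is evaluable regardless.
- **4.5.3.1 and 4.5.3.2, discontinuation.** Grade 4 events require stopping nivolumab, with a list of exceptions that includes asymptomatic lymphocytopenia. Section 4.5.3.1 carries that list over to ulocuplumab.
- **4.5.1.1 and 4.5.1.2, delay.** Ulocuplumab is delayed for drug-related events of Grade 3 or higher, "except for Grade 3 AEs that do not require nivolumab dose delay". The matching nivolumab exception reads "Grade 3 lymphocytopenia not associated with symptoms or clinical manifestations does not require dose delay". Grade 4 is not mentioned.
- **Table 4.5.2.1-1.** The first row takes all drug-related events of Grade 3 or higher, "except for Grade 3 hematologic AEs listed below or other exceptions listed in section 4.5.1". At DL1, DL2 and DL3A/3B the first event leads to resumption at 200, 400 and 800 mg weekly. At DL-1 the cell reads "1st event: Discontinue ulocuplumab". The only Grade 4 row is for asymptomatic lipase or amylase: hold, then resume at the same dose.
- **4.5.2.1, introduction to the table.** Modifications are allowed, not required, and depend on the nature of the event. The Medical Monitor is to discuss causality.

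SAP 2.1.1 repeats the DLT list but omits the cross-references to 4.5.3.1 and 4.5.3.2 from the discontinuation bullet. SAP 2 says that DL-1 has been opened after more than 2 DLTs at DL1, that no ulocuplumab reductions were reported at DL1, and that DL-1 allows none.

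**The concern.** An event that the protocol chose not to count as a DLT can return as one through the dose-modification table. At DL-1 the table can also take a subject off ulocuplumab for an event that 4.5.3.1 says does not require it.

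DLT incidence is the primary safety endpoint of this period (Protocol 8.3.1). DL-1 is judged separately for each tumor type. Two DLTs in up to 6 evaluable subjects make it intolerable, and an unacceptable DL-1 ends enrollment for that tumor type (3.1.1). Two sites following different sections could classify the same subject differently, and the cohort decision could turn on that choice.

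**Working it through.** No figure in the plan needs reproducing. The check traces the event through the rules, then applies the cohort rules of 3.1.1.

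**Trace**

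| Question | Source | Answer |
|---|---|---|
| DLT by the Grade 4 bullet? | 3.1.4 | No, excepted |
| Discontinuation required? | 4.5.3.1, 4.5.3.2 | No, excepted |
| Ulocuplumab delayed? | 4.5.1.1, 4.5.1.2 | Yes, exceptions are Grade 3 only |
| In the table's first row? | Table 4.5.2.1-1 | Yes: not a listed Grade 3 hematologic event, and not a 4.5.1 exception |
| Action at DL1 and above | First row | Resume at a lower dose |
| Action at DL-1 | First row | Discontinue at first event |
| DLT through that action? | 3.1.4 | Reduction within the 6 weeks: yes. Discontinuation: arguable |

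The discontinuation bullet is arguable because the protocol version points to 4.5.3.1, which excepts the event, while the SAP version has no pointer.

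**Comparison with the other event excepted in 3.1.4.** Asymptomatic Grade 4 amylase or lipase is also excepted from delay at Grade 3 only (4.5.1.2), but the table gives it a row that resumes at the same dose. Between these two events, the gap is specific to lymphocytopenia.

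**Other Grade 4 exceptions in 4.5.3.2.** These are corrected electrolyte abnormalities, thrombocytopenia or neutropenia under 5 days, asymptomatic leukopenia, and controlled endocrinopathy (with Medical Monitor approval). None has its own row, so at DL-1 each meets the same discontinue cell. 3.1.4 does not except them from its severity bullets, so for them the open question is whether drug stops, not whether a DLT is counted.

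**Effect of one extra counted DLT.** Rules of 3.1.1: 2 or more DLTs is intolerable; 0 in 3 to 6, or 1 in 6, is tolerable; 1 in 2 to 5 keeps enrolling. Assume that the affected subject has no other DLT and would otherwise stay evaluable, so k/n becomes (k+1)/n.

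- 0/3, 0/4, 0/5 become 1/3, 1/4, 1/5: tolerable becomes keep enrolling, with up to 3, 2 or 1 more subjects.
- 0/6 becomes 1/6: still tolerable.
- 1/6 becomes 2/6: tolerable becomes intolerable.
- 1/2, 1/3, 1/4, 1/5 become 2/2, 2/3, 2/4, 2/5: keep enrolling becomes intolerable.

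So 4 of the 5 tolerable outcomes change. This describes how the rule reacts to any one extra DLT; it does not estimate how often this event occurs.

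**If the stop is not counted as a DLT.** A subject stopped before the fifth ulocuplumab dose has at most 4 of 6 doses, below the required 5. That subject is not evaluable and is replaced. A 1/6 then becomes 1/5, which means one more subject.

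**What the hold does by itself.** Even the same-dose row holds drug until recovery, and skipped doses are not replaced (4.5.1.1). Take weekly dosing on schedule and delay as the interval since the last dose minus 7 days, the definition in SAP 7.4.2.2 (written for exposure reporting).

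- One missed dose: 6 − 1 = 5 doses, evaluable; delay 14 − 7 = 7 days.
- Two missed: 6 − 2 = 4 doses, not evaluable; delay 21 − 7 = 14 days, not more than 14.
- Three missed: delay 28 − 7 = 21 days, a DLT by the delay bullet if it falls within the period.

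**The case against.** The strongest reply is that the sections form layers. Being excepted from one DLT bullet does not exempt an event from the others, and an event that does not require discontinuation may still be stopped under another rule. At DL-1 no lower dose exists, so a reduction naturally becomes a stop. The introduction to the table is permissive, and causality must be documented by the investigator and discussed with the Medical Monitor.

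Part of this stands. A reader might infer that the table flatly contradicts 4.5.3.1, or that it makes the DLT automatic. The documents do not support that: 4.5.3.1 says when stopping is required and does not forbid it otherwise, and 4.5.2.1 leaves room for judgment.

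The layered reading does not explain the lipase and amylase row. The protocol gave the only other event excepted in 3.1.4 a same-dose resumption, which protects its DLT exception from the reduction and discontinuation bullets. Without such a row, the lymphocytopenia exception does little wherever the table is followed within the 6 weeks. Discretion also does not settle the matter, because neither document says which section prevails.

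Other mitigations are fair. Medical Monitor consultation is recommended for Grade 4 lymphocytopenia, all available safety data are considered (Protocol 8.4.3, SAP 7.6.1), intolerability stops enrollment for evaluation, and over-counting errs toward caution. The missing pointer in the SAP is a small matter alone, since the operative words are otherwise the same. The table's second row reads irregularly in the public copy; nothing here rests on it.

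**Conclusion.** The conflict is real and worth fixing, within limits. The rules give no single answer on whether asymptomatic drug-related Grade 4 lymphocytopenia leads to a reduction or stop of ulocuplumab, and hence whether it counts as a DLT. No probability can be attached, because the documents give no rate for the event.

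The live route is DL-1. There the largest single consequence is 1/6 becoming 2/6 at a level with no dose below it, assuming that the table is followed and the stop is counted.

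Two further inferences should be resisted. One is that this gap contributed to the DLTs at DL1: the SAP reports no ulocuplumab reductions there, and neither document reports such an event at any level. The other is that the discontinuation conflict concerns lymphocytopenia alone: at DL-1 it extends to the other Grade 4 exceptions in 4.5.3.2. Whether the exception or the table reflects the intended clinical rule is for the sponsor to say.

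**What to change.** If the exception in 3.1.4 is the intended rule:

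1. Add asymptomatic Grade 4 lymphocytopenia to the row of Table 4.5.2.1-1 that resumes at the same dose.
2. State in 3.1.4 and SAP 2.1.1 that events excepted from the Grade 4 bullet are not DLTs through the reduction or discontinuation bullets, and restore the cross-references in SAP 2.1.1.
3. State how the hold, the delay bullet beyond 14 days and the 5-of-6-dose rule apply to these events. One option is to extend the lymphocytopenia delay exception in 4.5.1.2 to Grade 4. Section 4.5.1.1 would then need the same change, since its carry-over is limited to Grade 3. Without this step, the table edit alone leaves loss of evaluability and a delay DLT possible.
4. Exclude the Grade 4 exceptions of 4.5.3.2 from first-event discontinuation at DL-1, or state that 4.5.3.1 prevails.

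The cost is wording in the table, 3.1.4, 4.5.1 and SAP 2.1.1, with no added subjects. Any DL-1 DLT call or ulocuplumab discontinuation already made for this event should be re-checked.
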